# 5.3 DISPENSING

Participating centres will be provided with a start-up supply of trial medication once the institution has been approved for participation in Add-Aspirin (see section 2). Packs of trial treatment will be labelled with a code to maintain blinding. Once received in the pharmacy, the drug should be kept in a dry, safe place according to the Summary of Product Characteristics (SPC). Trial-specific working

practices will be supplied to the centre pharmacist in the Drug Supply Management System (DSMS) user guide.

The trial medication must only be used to treat participants in the Add-Aspirin trial. Both the run-in period tablets and tablets for randomised patients should be taken from Add-Aspirin trial stock only and should be dispensed via DSMS (including open-label run-in packs).

Only the Investigator or a person assigned by them that has been appropriately trained and assigned on the delegation log to do so, will be allowed to prescribe the drug to the participant. Institutions will be given guidance on re-supply in the drug supply manual.

# 5.4 DOSE MODIFICATIONS, INTERUPTIONS & DISCONTINUATIONS

Aspirin is a licensed, generic drug which has been in use for many years and the safety profile is well documented. Rates of toxicity are low in comparison with other adjuvant therapies. Where appropriate, prophylactic measures can be used to reduce the risk of toxicity. Suggested management principles for events and toxicities during the trial can be found below. Toxicities will be graded using the CTCAE v4 (see appendix II) and the SPC can be consulted for further information.

### **5.4.1 POSSIBLE TOXIC EFFECTS**

In order to avoid unblinding, wherever possible, Investigators should investigate and manage toxicities under the assumption that the participant is receiving 300mg aspirin. See section 5.6.1 for further information on unblinding. Possible toxicities as detailed in the SPC for Bayer aspirin tablets are as follows (please note this list does not include all known toxicities):

# Table 4. Terminology used for the frequency of aspirin toxicities

Very common: $\geq$ 1/10 patients	
Common: $\geq$ 1/100 to < 1/10 patients	
Uncommon: $\geq$ 1/1,000 to < 1/100 patients	
Rare: ≥ 1/10,000 to < 1/1,000 patients	
Very rare: <1/10,000 patients	
Not known: frequency cannot be estimated from the available data	

# 5.4.1.A Blood and lymphatic system disorders

# Rare to very rare:

- Serious bleeding, such as cerebral bleeding, especially in patients with uncontrolled hypertension and/or concomitant treatment with anticoagulants, which in isolated cases may be potentially life-threatening, have been reported.
- Bleeding, e.g. nosebleeds, bleeding gums, cutaneous bleeding, menorrhagia or urogenital bleeding, possibly with prolongation of the bleeding time. This effect can persist for 4 to 8 days after use.

# 5.4.1.B Gastrointestinal disorders

Common:

- Gastrointestinal disorders such as dyspepsia (heartburn), nausea, vomiting, abdominal pain and diarrhoea.
- Minor blood loss from the gastrointestinal tract (microhaemorrhage).

#### Uncommon:

• Gastrointestinal ulcers which in very rare cases can lead to perforation.

- Gastrointestinal bleeding.
- Long-term use of aspirin may cause iron deficiency anaemia due to occult blood loss from the gastrointestinal tract.

Rare:

Severe gastrointestinal haemorrhage (e.g. requiring hospital admission)

# 5.4.1.C Nervous system disorders

Rare:

Intracranial haemorrhage.

#### Unknown:

 Headache, dizziness, vertigo, impaired hearing ability, tinnitus or mental confusion (these can be signs of an overdose).

#### 5.4.1.D Skin and subcutaneous tissue disorders

Common:

Increased risk of bruising

#### Uncommon:

Urticaria.

#### Rare:

- Erythema nodosum.
- Erythema multiforme.
- Steven Johnson Syndrome.
- Toxic epidermal necrolysis.

#### 5.4.1.E Immune system disorders

Rare:

- Hypersensitivity reactions of the skin, the respiratory tract and the gastrointestinal tract, particularly in asthma sufferers.
- Hypersensitivity reactions can lead to anaphylactic shock and angioedema.

# 5.4.1.F Hepatobiliary disorders

Very rare:

Transient elevated liver enzymes.

#### Unknown:

Hepatitis and hepatic insufficiency.

#### 5.4.1.G Renal and urinary disorders

Very rare:

Impaired kidney function.

#### 5.4.1.H Metabolism

### Very rare:

- Hypoglycaemia can occur with concurrent use of sulphonylurea antidiabetic medication.
- Hyperuricaemia At low doses acetylsalicylic acid reduces the excretion of uric acid. Aspirin should be used with caution in patients with gout as this may worsen, or cause an acute exacerbation of gout.

## 5.4.1.1 Eyes and vision Unknown: Macular degeneration.

It has been suggested that aspirin could be linked to an eye condition called age-related macular degeneration (age-related loss of sight), however evidence has been conflicting and this has not been confirmed.

# 5.4.2 PROPHYLACTIC MEASURES

Eligibility criteria have been formulated so that individuals with an increased risk of serious toxicity from aspirin are excluded. This risk is further mitigated by limiting those 75 years old or over to 100mg of aspirin (or matching placebo) and restricting concomitant use of other medications that increase the risk of serious toxicity (see appendix II).

The management of those experiencing dyspepsia during the trial is described in section 5.4.3.A. Patients experiencing dyspepsia prior to trial registration should undergo investigation and successful treatment (including *H.pylori* eradication where indicated) before enrolling in the Add-Aspirin trial. Investigators are referred to guidance on the management of dyspepsia from the UK National Institute for Health and Clinical Excellence (NICE), available from https://www.nice.org.uk/guidance/CG184 Smoking and regular use of alcohol are also known to increase the risk of dyspepsia and should be avoided.

For those who are asymptomatic, prophylactic measures to reduce the risk of gastrointestinal toxicity from aspirin, such as PPI prophylaxis and *H.pylori* eradication, are not routinely recommended in participants at low risk of GI complications and are not mandated in the Add-Aspirin protocol. However, in the UK and Republic of Ireland, PPI use for the duration of aspirin treatment is mandated for patients who have undergone oesophagectomy or gastrectomy and is also recommended for elderly patients (≥75 years), or any other participant who might be at increased risk of toxicity. In India, PPI use is as per local practice.

Intracranial bleeding is a rare toxicity of aspirin. Hypertension can increase the risk of an intracranial bleed. All participants should have blood pressure assessed prior to registration and throughout participation in the trial, in accordance with the assessment schedules. For information on the management of hypertension please refer to section 5.4.3.C.

For those participants who are due to undergo elective surgery, they should discuss withholding their trial medication with their surgeon for a period of time. If unplanned surgery is needed, emergency unblinding is available where knowledge of treatment allocation would alter management (see section 5.6).

# 5.4.2.A Prophylactic Use of Histamine Receptor Antagonists

Where an investigator feels it is clinically appropriate to use a histamine receptor antagonist in place of a proton pump inhibitor for patients at high risk of gastro-intestinal toxicity, or for the treatment of gastro-intestinal toxicity, this will be acceptable within Add-Aspirin. In patients who have undergone a gastrectomy or oesophagectomy in the UK and Republic of Ireland, a proton pump inhibitor should be used, however a histamine receptor antagonist would be an acceptable alternative where a proton pump inhibitor is contraindicated.

[figure not shown]
# 5.4.3 TOXICITY MANAGEMENT

Participants should be advised to immediately inform healthcare professionals if, at any time during the trial, they have a suspected heart attack, stroke, serious bleed or any other serious medical event, and inform the treating healthcare professional that they are in the Add-Aspirin trial. In particular, criteria where urgent referral for endoscopy and suspension of trial treatment may be appropriate include gastrointestinal bleeding (immediate referral if significant acute bleeding), progressive dysphagia, iron deficiency anaemia or persistent vomiting.

# 5.4.3.A Management of Dyspepsia

Dyspepsia is characterised by discomfort in the upper abdomen, often described as heartburn, which can be associated with bloating and occasionally nausea and vomiting. Dyspepsia can be caused or exacerbated by aspirin. For the management of dyspepsia or related symptoms please follow the flow diagram (see figure 2) and corresponding notes. Please also refer to NICE guidelines.

These notes refer to the points on the management of dyspepsia flow diagram (figure 2).

a. The trial treatment should be withheld whenever there are moderate or severe symptoms of dyspepsia (CTCAE v4 grade  $\geq$  2) or whenever symptoms are unacceptable to the

participant. The clinical decision to withhold trial treatment should be recorded in the relevant section on the Follow-Up CRF (Form 8).

- b. All participants with grade ≥ 2 dyspepsia should undergo *H.pylori* testing. Where there is an indication for upper gastrointestinal endoscopy, *H.pylori* testing should be performed at the same time. Otherwise *H.pylori* testing can be performed by a carbon-13 urea breath test or stool antigen test (a two week PPI wash out period is required before breath or stool antigen testing) or can be performed by laboratory based serology where the test has been locally validated. Any participant found to be *H.pylori* positive should undergo eradication therapy according to local protocols.
- c. Where indicated upper gastrointestinal endoscopy should be performed. For indications please refer to the UK NICE guidelines for the management of dyspepsia.
- d. A proton pump inhibitor (PPI) should be initiated or continued for the whole trial period where no contraindication exists. The dose should be titrated up where symptoms persist to a maximum dose according to the British National Formulary (BNF).
- e. Review medications for any other causes of dyspepsia (e.g. calcium antagonists or bisphosphonates) and offer life-style advice (see NICE dyspepsia guidelines).
- f. Where dyspepsia reoccurs or worsens (CTCAE v4 grade ≥ 2) after the trial treatment has restarted consider upper gastrointestinal endoscopy particularly if this has not already been performed and increase PPI therapy to a maximum dose according to the BNF.
- g. Those on the higher dose of trial treatment can have their dose reduced (dose level-1). MRC CTU at UCL will arrange for those taking 300mg aspirin or matched placebo to be reissued with 100mg aspirin or matched placebo. Those already taking 100mg aspirin or matched placebo will permanently discontinue the trial treatment.
- h. Where the trial treatment is withheld for more than a total of 3 months the trial medication should be permanently discontinued. In the run-in period aspirin should be permanently discontinued if withheld for more than a total of 4 weeks.
- i. Wherever the trial treatment has been permanently discontinued, follow-up in the trial should continue. Participants in the run-in period will be asked for consent to allow passive follow-up data collection using medical records.

# 5.4.3.B Management of Gastrointestinal Bleeding

Aspirin induced bleeding can occur anywhere in the gastrointestinal tract but most commonly occurs from the stomach or oesophagus. Symptoms and signs of bleeding include dark tarry stools, vomiting of blood, either in the form of fresh blood or altered blood (often a coffee colour and consistency). Iron deficiency anaemia, both acute and chronic, is also an indication for investigation to exclude gastrointestinal bleeding. Where a participant develops significant gastrointestinal bleeding (grade 3 or 4) whilst taking the trial medication it should be permanently discontinued. Where significant gastrointestinal bleeding (grade 3 or 4) occurs in the trial run-in period, aspirin should be permanently discontinued and participants should not be randomised. For guidance on the management of acute upper gastrointestinal bleeding please refer to the NICE guidelines for the bleeding,(NICE management of gastrointestinal CG141), available from: http://guidance.nice.org.uk/CG141/NICEGuidance/pdf/English.

For less significant episodes of gastrointestinal bleeding (grade 1 or 2) – particularly if the cause is not directly related to aspirin/trial medication, clinical discretion should be applied as to whether trial treatment should be discontinued. Individual cases can be discussed with clinical members of the trial management group by contacting the MRC CTU at UCL. Trial medication can be withheld (for up to 3 months) while clinical investigations/decisions are considered.

# 5.4.3.C Management of Other Toxicities

Any of the following toxicities should result in the trial medication being immediately and permanently discontinued:

- Gastrointestinal bleeding (grade 3 or 4)(see section 5.4.3.B)
- Active gastrointestinal ulceration
- New or worsening tinnitus or hearing loss (grade 2 or above)
- Intracranial bleeding
- Hypersensitivity to aspirin
- Other toxicities can be discussed with MRC CTU at UCL

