# 5 TREATMENT OF PARTICIPANTS

# 5.1 TREATMENT DURING THE RUN-IN PERIOD

See section 4.2 for when the run-in period can commence. All participants will take 100mg aspirin (open-label) once daily for approximately 8 weeks (7-9 weeks is acceptable) prior to randomisation in order to identify those individuals who are unlikely to be able to tolerate aspirin and those who are unlikely to be able to adhere to the protocol treatment regimen. The guidance on investigating and managing treatment toxicity, provided in the subsequent sections, should be followed during the active run-in period as well as during randomised treatment in the trial. Dose reductions will not be relevant during the run-in period and so treatment should be discontinued in the event of significant toxicity.

At the end of the run-in period, treatment adherence and toxicities will be assessed, as described in section 6.2, to identify those participants who are suitable to be randomised into the trial. Participants that experience any aspirin-related severe toxicity (defined as  $\geq$ grade 3 Common Terminology Criteria for Adverse Events (CTCAE v4)) or significant gastrointestinal bleeding (grade 3 and 4), active gastrointestinal ulceration, new cases or worsening tinnitus (grade 2 or above), , intracranial bleeding or hypersensitivity to aspirin should permanently discontinue aspirin immediately and will not be eligible for the trial.

As described in section 6.2, if the Investigator feels that the reason for inadequate adherence is temporary, the run-in period may be extended by 4 or 8 weeks to reassess adherence and toxicity. All extensions to the run-in period must be discussed with the Trial Manager and the trial medication will be resupplied accordingly.

No 'wash-out' period will be necessary between the run-in period and randomisation and the blinded medication should be commenced as close to the end of the run-in period as possible.

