# 6.2 PROCEDURES FOR ASSESSING SUITABILITY FOR RANDOMISATION FOLLOWING THE RUN-IN PERIOD

Assessments at the end of the run-in period will focus on treatment adherence and toxicity in order to determine the participant's suitability for randomisation into the trial. Participants will be provided with a diary card to complete during the run-in treatment period. They will be asked to bring this, along with their used blister packs, to their subsequent visit and these will be used to assess adherence. Toxicity will be assessed and documented using CTCAE v4 as for all other follow-up visits. Other assessments at this time include a blood test, blood pressure and an update on usage of concomitant medications, all of which will be assessed as described in section 6.4 for other follow-up visits.

The run-in period should be 7-9 weeks long. Participants will be suitable for randomisation if they have taken at least 80% of their run-in treatment (6 or 7 tablets per week) and have not experienced any aspirin-related severe toxicity (defined as ≥grade 3 CTCAE v4), nor significant gastrointestinal bleeding (grade 3 or 4), active gastrointestinal ulceration, new cases or worsening tinnitus (grade 2 or above), intracranial bleeding or hypersensitivity to aspirin. The Investigator is responsible for the final decision as to whether participants are suitable to be randomised but the Trial Management Group will be available for discussion via the Trial Manager if there are concerns or uncertainties.

The run-in period can be extended where the Investigator decides there is a valid reason for inadequate adherence (e.g. unforeseen social circumstances), or the cause of inadequate adherence is temporary (e.g. reversible dyspepsia, see section 5.4.3.A). Additionally this may apply to patients who may be eligible for CAPP3 and are awaiting results of genetic testing. Where offered, the run-in period would normally be extended by 4 or 8 weeks after which adherence and toxicity would be reassessed in the same way. All extensions to the run-in period must be pre-approved by MRC CTU at UCL via the Trial Managers and only one extension for a maximum of 8 weeks is permitted per participant.

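### Hearing loss of grade 2 or above stops trial medication permanently under 5.4.3.C but is missing from the run-in lists in 5.1 and 6.2, so the three lists conflict

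*Protocol*

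**What the plan says.** Section 5.4.3.C introduces its list with "Any of the following toxicities should result in the trial medication being immediately and permanently discontinued". One entry is "New or worsening tinnitus or hearing loss (grade 2 or above"). The other named entries are gastrointestinal bleeding of grade 3 or 4, active gastrointestinal ulceration, intracranial bleeding and hypersensitivity to aspirin.

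Section 5.1, on the run-in, states: "The guidance on investigating and managing treatment toxicity, provided in the subsequent sections, should be followed during the active run-in period". It then gives its own list of events after which run-in aspirin is stopped permanently and the participant is ineligible. The end of that list reads "new cases or worsening tinnitus (grade 2 or above), , intracranial bleeding or hypersensitivity to aspirin".

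Section 6.2 sets the suitability rule: "Participants will be suitable for randomisation if they have taken at least 80% of their run-in treatment" and "have not experienced any aspirin-related severe toxicity", defined as grade 3 or above, nor any of a set of named events. That set ends with "new cases or worsening tinnitus (grade 2 or above), intracranial bleeding or hypersensitivity to aspirin".

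Section 5.4.1.C names impaired hearing beside tinnitus among the possible toxicities of aspirin, with frequency unknown.

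**The concern.** Sections 5.1 and 6.2 appear to mirror 5.4.3.C, but one trigger has dropped out of both. Because 5.1 brings the later toxicity guidance into the run-in, the two rules apply to the same person at the same time. One says the drug must be stopped for good. The other, read as a checklist, has no entry that would keep that person from being randomised.

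The run-in exists to identify people unlikely to tolerate aspirin or to adhere to it. If a site works from the 6.2 list alone, a participant with grade 2 hearing loss could go forward. Once randomised, the chance of active aspirin is 2/3 (1:1:1 under 75 years, 2:1 at 75 or over). Under 75 that includes a 1/3 chance of 300mg after a run-in at 100mg. Sites that read 5.4.3.C first and sites that read 6.2 first could treat the same event differently.

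**Working it through.** No sample size, power or error-rate figure is involved. The check is a comparison of the lists, followed by a short calculation on the adherence rule.

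**Step 1. Compare the three lists.**

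| Trigger | 5.4.3.C (permanent stop) | 5.1 (run-in stop, ineligible) | 6.2 (not suitable) |
|---|---|---|---|
| GI bleeding, grade 3 or 4 | yes | yes | yes |
| Active GI ulceration | yes | yes | yes |
| Tinnitus, grade 2 or above | yes | yes | yes |
| Hearing loss, grade 2 or above | yes | **not named** | **not named** |
| Intracranial bleeding | yes | yes | yes |
| Hypersensitivity to aspirin | yes | yes | yes |

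Hearing loss is the only named trigger that differs, and it is missing from both run-in lists.

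**Step 2. Does the general clause catch it?** The clause in 5.1 and 6.2 covers aspirin-related toxicity of grade 3 or above. Aspirin-related hearing loss of grade 3 or above is therefore caught. Grade 2 is not.

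**Step 3. Does 5.4.3.C apply in the run-in?** Yes. Section 5.1 says the later toxicity guidance is to be followed then, and section 7.1.1 counts the run-in aspirin as an investigational product.

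**Step 4. Who passes the 80% rule?** Inputs from 6.2 and 4.1: a run-in of 7 to 9 weeks at one tablet a day. Tablets needed = 0.8 × run-in days, rounded up.

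- 7 weeks: 0.8 × 49 = 39.2, so 40 tablets
- 8 weeks: 0.8 × 56 = 44.8, so 45 tablets
- 9 weeks: 0.8 × 63 = 50.4, so 51 tablets

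A participant with no missed doses who stops at once still meets the rule if onset falls after about day 40, 45 or 51 respectively. If the event is first recorded at the end-of-run-in visit, all tablets may have been taken and the rule is met. With earlier onset and an immediate stop, the participant fails on adherence, so the gap in the list does not matter.

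**Step 5. Combine.** A participant with late-onset or late-recorded grade 2 hearing loss, and no other listed event, meets every listed criterion in 6.2 and is also subject to permanent discontinuation under 5.4.3.C.

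**The case against.** The strongest reply is that the protocol, read as a whole, would not let such a participant be randomised.

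- **The stop already binds in the run-in, and discontinuation has its own route.** Note (i) in 5.4.3.A and the closing bullet under the other-toxicity heading in 5.4.3.C send people who discontinue during the run-in to passive follow-up. Under 4.1 that is the route for those not randomised. This is a fair account of the likely intent. But the first text concerns dyspepsia and the second concerns toxicities outside the permanent-stop list, so for hearing loss the pathway is implied, not stated. For serious gastrointestinal bleeding, 5.4.3.B spells out both the permanent stop and the bar on randomisation.
- **Judgement remains.** Section 4.3 requires that the participant be felt suitable for long-term aspirin, and 6.2 gives the Investigator the final decision with the Trial Management Group available. This stands as a safeguard. It is discretionary, and 4.3 refers back to 5.1, whose list omits hearing loss.
- **The exclusion criteria.** Every cohort excludes a past adverse reaction to aspirin (3.2, 3.4, 3.6, 3.8), and 4.3 requires that no exclusion criterion be met at randomisation. Taken literally, that would cover aspirin-related hearing loss. It cannot be meant to bar every run-in reaction, however, because 6.2 allows an extension for reversible dyspepsia.

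A reader might go further and infer that everyone with grade 2 hearing loss in the run-in counts as suitable. The documents do not support that: early onset with an immediate stop fails the 80% rule, and the safeguards above may hold back the rest. A reader might also infer that avoidable early stops would dilute the intention-to-treat comparison. No frequency is given to support that. Nor is it clear that a stable deficit carried over from the run-in would count as new or worsening after randomisation.

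**Conclusion.** The inconsistency is real. For hearing loss of grade 2, section 5.4.3.C requires permanent discontinuation, while the lists in 5.1 and 6.2 do not make the participant ineligible or unsuitable.

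The group affected is narrow: grade 2 hearing loss, at least 80% of run-in tablets taken, and no other listed event. The onset days of about 40, 45 and 51 assume one tablet a day, no earlier missed doses, an immediate stop, and no extension of the run-in. The 2/3 chance of active aspirin is simply the allocation ratio. It matters only if a site randomises despite 5.4.3.C and the judgement called for in 4.3 and 6.2.

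No number of participants can be stated, and the effect on the efficacy comparison is likely negligible. The point rests on participant protection and on sites applying one eligibility rule. It is worth correcting because the contradiction is plain and nearly free to remove.

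**What to change.** Reconcile 5.1, 5.4.3.C and 6.2 so that the three lists agree on hearing loss. Whether and at what grade it belongs in them is for the trial's clinical leads to decide; this review takes no position. The simplest safeguard against a repeat is to keep one list and have the other two sections refer to it.

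The cost is a few words in 5.1 and 6.2, or in 5.4.3.C, at the next amendment. The end-of-run-in form (Form 7), whose content is not shown, should be checked for the same omission. No analysis or sample size changes.
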